**Table 7. Clinical Laboratory Evaluations**

Hematology	
Hemoglobin	Platelet count
Hematocrit	WBC count with differential
RBC count	High sensitivity C-reactive protein (hsCRP)
Reticulocyte count	Hemoglobin Electrophoresis (at Baseline only)
Serum Chemistry	
Blood urea nitrogen	Alanine transaminase (ALT/SGPT)
Creatinine	Aspartate aminotransferase (AST/SGOT)
Electrolytes with glucose	Fractionated bilirubin
	Lactate dehydrogenase (LDH)
Urinalysis	
pH	Bilirubin
Specific gravity	Blood
Protein	Nitrite
Glucose	Urobilinogen
Ketones	Leukocyte esterase

#### **6.3.4 Pregnancy Test**

A pregnancy test (urine or serum at the discretion of the investigator) is required for women of childbearing potential. Females who are surgically sterilized for at least 6 months OR more than 2 years postmenopausal can be excluded from this requirement.

Any pregnancies occurring during the study will be handled as described in Section 6.3.6.5.

#### **6.3.5 Adverse Events and Serious Adverse Events**

AEs and SAEs will be reviewed on an ongoing basis by the Sponsor Medical Monitor to identify safety concerns. Relevant safety issues will be communicated to participating investigator(s) and regulatory agencies as appropriate.

##### **6.3.5.1 Definition of Adverse Events**

An AE is any untoward medical occurrence in a subject administered a pharmaceutical product that does not necessarily have a causal relationship with this treatment. Adverse events may be reported by the subject, discovered by investigator questioning, or detected through physical examination, laboratory test, or other means.

AEs include (International Conference on Harmonization E2A):

- Any new undesirable medical experience or an unfavorable and unintended change of an existing condition that occurs during or after treatment, whether or not considered related to study drug
- Abnormal laboratory findings considered by the investigator to be clinically significant, ie, those that are unusual for the populations being studied or individual subject

The subjects will be instructed to inform the investigator or clinical staff of any AEs and intercurrent illnesses experienced during the trial. The inquiry will be posed in a non-specific manner using open-ended questions so as not to bias the response (eg, “How are you today?” or “How have you been since your last visit?”). Any subject who has an AE will be evaluated by the investigator and will be treated.

### **6.3.5.2 Grading of Adverse Events**

Each sign or symptom reported will be graded in accordance with the World Health Organization (WHO) Common Toxicity Criteria (Appendix 1). The date of AE onset, time of onset, duration, severity, relationship, outcome, and use of concomitant treatment will be recorded for each event.

Except as noted below, the following severity classifications will be used if the AE does not have a toxicity grade listed in Appendix 1.

- Mild: The AE is of little concern to the subject and/or of no clinical significance. The event is not expected to have any effect on the subject’s health or well-being.
- Moderate: The subject has enough discomfort to cause interference with or change in usual activities. The event is of some concern to the subject’s health or well-being. The event may require medical intervention.
- Severe: The subject is incapacitated and unable to work or participate in many or all usual activities. The event is of definite concern to the subject and/or poses substantial risk to the subject’s health or well-being. The event is likely to require medical intervention and/or close follow up.

The investigator (a study physician listed on Form FDA 1572) will review each event and assess its relationship to drug treatment (unrelated, possibly related, or probably related). The investigator should decide whether, in his or her medical judgment, there is a reasonable possibility that the event may have been caused by the investigational product.

The relationship of each AE to study drug will be assessed using the following guidance:

- Unrelated: The event can be readily explained by other factors such as the subject’s underlying medical condition, concomitant therapy, or accident and no obvious temporal relationship exists between the investigational product and the event.

- Possibly related: There may be some temporal relationship between the event and the administration of the investigational product but there remains some ambiguity as to the cause.
- Probably related: The temporal relationship between the event and the administration of the investigational product is compelling, and/or follows a known or suspected response pattern to that product, and the event cannot be explained by the subject's medical condition, other therapies, or accident.

The outcome may be classified as follows:

- Resolved: The subject has fully recovered from the event with no residual effects observable.
- Stabilized: Effects of the event are constant. The likelihood of these effects changing (improving or worsening) is low.
- Ongoing: Effects of the event are still present and changing. The event is not considered stabilized or resolved.
- Death Due to Eventii: The event was the primary cause of death (may or may not be the immediate cause of death).
- Death Due to Other Event: The subject died but the event reported was not the primary cause of death.

### 6.3.6 Recording and Period of Observation

All AEs and SAEs occurring from time of first study procedure (informed consent, and assent, where applicable) through day 28 ± 5 post last dose will be collected and recorded in the source document. All AEs and SAEs occurring from first dose of study drug through day 28 ± 5 post last dose will be collected and recorded on the CRF, whether or not they are considered to be related to study medication. Whenever possible, recognized medical terms should be used. If the investigator is confident of a unified diagnosis, all related signs, symptoms, and abnormal laboratory test results are to be grouped together as a single AE on the CRF (eg, cough and rhinitis are to be reported as "upper respiratory tract infection"). However, signs and symptoms considered unrelated to a syndrome or disease are to be reported as individual events.

Clinically significant worsening of pre-treatment untoward events, after initiation of study drug, must be reported as new AEs.

Adverse events occurring secondary to other events are to be identified by the primary cause. Death is an outcome of an event. The event that resulted in death should be recorded on the AE page of the CRF.

For hospitalizations for surgical or diagnostic procedures, the illness leading to the procedure is to be recorded as an SAE. The procedure is to be documented in the narrative as "action taken" in response to the illness.

ii Death is an outcome of an event and not an event per se (sudden death or death of unexplainable causes can be reported but follow-up will be required until cause of death is determined).

Following discharge from the hospital, if the AE is still not resolved, the subject will be referred to the subject's own physician, and followed up until the findings return to normal or acceptable levels, as judged by the investigator. Where appropriate, medical tests and examinations will be performed to document resolution of event(s).

All AEs will be followed to resolution (the subject's health has returned to his/her baseline status or all variables have returned to normal), an outcome is reached, stabilization (the investigator does not expect any further worsening of the event), or the event is otherwise explained, regardless of whether or not the subject is still participating in the study. Where appropriate, medical tests and/or examinations will be performed to document resolution of events.

#### **6.3.6.1 Disease Related Adverse Events (DRAEs)**

It is recognized that VOC and pain are frequent and expected events in SCD, and will be present at baseline in all subjects enrolled in this study. Fluctuations in pain are the expected and usual course of VOC and will not be reported as AEs. Pain and fluctuations in pain will be collected as part of the primary study objective, and evaluated extensively in the efficacy analysis. Changes in pain resulting from causes other than VOC should be reported as AEs. The use of opioids for VOC episodes is usually required and considered routine. Subjects being admitted to the hospital for VOC will be expected to receive IV opioid or IV pain medications for treatment of the VOC. It is also recognized that subjects being discharged from the hospital for VOC will go home with prescribed opioid and other pain medications.

After discharge from the hospital following a VOC episode, subjects often have recurrent or repeat episodes of VOC. For the purposes of this study, after discharge from the hospital for the original event, VOC (new or recurring) shall be defined as an episode requiring a visit to a medical facility resulting in medical treatment for pain. When determining grade of an AE for new or recurring VOC, the investigator shall use the classification noted below.

- Mild: the pain can be managed at home (includes home oral opioid pain medication)
- Moderate: the pain requires medical intervention (includes clinic, day hospital, or emergency department care)
- Severe: the pain requires inpatient treatment

Patients with SCD, as a result of this condition, commonly have abnormal laboratory values and clinical findings. It is assumed that abnormalities in physical exam or laboratory findings consistent with the subject's underlying diagnosis of SCD or VOC will be present prior to dosing and therefore will not be treatment-emergent AEs (TEAEs).

In general, symptoms of SCD should not be classed as AEs if they are within the normal day-to-day fluctuation expected for the disease. However, significant

worsening of the symptoms should be recorded as an AE. Therefore, DRAEs that are also TEAEs will be reported as AEs per study procedures.

### **6.3.6.2 Vital Signs and Clinical Laboratory Evaluations**

Abnormal vital signs are not to be considered AEs unless thought to be clinically significant by the investigator or treating physician.

Abnormal laboratory values which are out of range and clinically significant and which are a worsening from the subject's baseline should be reported as AEs. When evaluating such changes, the extent of deviation from the reference range or a subject's baseline value, the duration until return to the reference range/baseline, either while continuing treatment or after the end of treatment with the investigational product, and the range of variation of the respective parameter within its reference range, must be taken into consideration.

The investigator should decide, based on the above criteria and the clinical condition of a subject, whether a change in a vital sign or laboratory parameter is clinically significant and therefore represents an AE.

The Sponsor Medical Monitor will routinely evaluate clinical laboratory findings and vital signs to investigate possible emerging trends.

### **6.3.6.3 Serious Adverse Event**

An SAE is any untoward medical occurrence that:

- Results in death
- Is life-threatening
- Results in permanently disabling or incapacitating condition
- Requires inpatient hospitalization
- Prolongs inpatient hospitalization
- Is a congenital anomaly/birth defect
- Is an important medical event that may not result in death, be life-threatening, or require hospitalization but which, based upon appropriate medical judgment, may jeopardize that subject and may require medical or surgical intervention

All SAEs will be reported by the investigational staff to the contract research organization (CRO) SAE Hotline within 1 working day of their knowledge of the event and followed by a written report within 2 working days, whether or not the SAEs are deemed drug-related.

If an SAE occurs, the CRO SAE Hotline is to be contacted immediately (refer to contact information in the Study Reference Manual).

The initial report of an SAE should include the following minimum information: an identifiable subject; the study drug; an identifiable reporting source; and an event or

outcome that can be identified as serious. The investigator or designee must also inform the Institutional Review Board (IRB)/Independent Ethics Committee (IEC), in compliance with GCP and local IRB/IEC reporting guidelines, of an SAE, whether or not considered study-related. The initial written report to the CRO and to the IRB/IEC must be as complete as possible.

Questions regarding safety issues and any SAEs may be directed to the SAE Hotline or the CRO Medical Monitor (refer to contact information in the Study Reference Manual).

If deemed appropriate for medical treatment decision-making purposes, the randomization assignment for individual subjects may be unblinded (refer to Section 5.1.5 for details of unblinding).

The Sponsor will be responsible for reporting SAEs to regulatory agencies (FDA, Health Canada, or other national or foreign regulatory authorities) as required.

#### **6.3.6.4 Dose Limiting Toxicities and Study Stopping Rules**

Dose-limiting toxicity will be defined as treatment-emergent SAEs deemed by the Sponsor Medical Monitor and Data Safety Monitoring Board (DSMB) to be related to study drug per this protocol, and to reach a level of significance for the study that requires investigation before proceeding with further enrollment or dosing in the study.

The Sponsor Medical Monitor will perform ongoing review of all SAEs in a timely fashion, and will perform frequent reviews of all AEs and lab data in the study. Any concerns for safety identified by the Medical Monitor will be communicated to the DSMB for review.

An interim safety review will be performed by the DSMB and Sponsor Medical Monitor after treatment of the first 10 subjects under age 18 years, and additionally after 25 and 50 subjects of all ages have been treated with the study drug. This review will include AEs and any other pertinent information. There will be 2 levels of review. First, the Sponsor Medical Monitor and DSMB will review safety data in a blinded fashion, to identify any possible concerns. Second, the DSMB will hold a closed meeting to review safety data by treatment group. The DSMB Chair will have the option to request a fully unblinded review by the DSMB of any data deemed appropriate. The Medical Monitor will not attend an unblinded data review meeting. If any safety concerns arise, the DSMB will make a recommendation to the Sponsor Medical Monitor on how to proceed.

Enrollment in the study will be temporarily halted for further review of safety data if the following are seen and deemed to be possibly or probably related to study drug. This further assessment of safety data will include review by the DSMB, which may ask for blinded or unblinded data at the discretion of the Chair of the DSMB. The

Sponsor Medical Monitor and Coordinating Investigator may also take part in this review, but not in a manner that would unblind either of these individuals. Events that would trigger halting enrollment and a more in-depth safety review include:

- >30% of subjects with recurrent VOC requiring hospitalization within 7 days of discharge for the current study
- >30% of subjects with documented systemic bacterial infections in normally sterile sites (excluding uncomplicated urinary tract infection and otitis media)
- >5% of subjects with death from SCD-related cause or other medical cause during the study or within 28 days of last dose of study drug

In addition, the study may be halted for further review:

- If, for any reason involving safety, the investigator deems continuing the study inappropriate, and halts the study at that site
- If, for any reason, the Sponsor deems continuing the study inappropriate

If the study is halted temporarily or terminated, a written statement fully documenting the reasons for study halt or termination will be provided to the IRB/IEC and appropriate regulatory authorities.

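### The enrolment-halt thresholds name disease outcomes but count them only when judged drug-related, which makes them insensitive if a sizeable share of cases is graded unrelated

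*Protocol*

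**What the plan says.** Section 6.3.6.4 halts enrolment temporarily, pending a fuller safety review, "if the following are seen and deemed to be possibly or probably related to study drug". Three frequency criteria follow:

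- ">30% of subjects with recurrent VOC requiring hospitalization within 7 days of discharge for the current study";
- systemic bacterial infection, documented at a site that is normally sterile, in over 30% of subjects, leaving out uncomplicated urinary infection and otitis media;
- ">5% of subjects with death from SCD-related cause or other medical cause during the study", with the window running to 28 days after the last dose.

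The section does not say who makes the relatedness judgment for these criteria. The review that follows includes the DSMB, which may ask for unblinded data.

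Section 6.3.5.2 defines the grades. Unrelated has two limbs joined by *and*: other causes readily account for the event, and nothing obvious links it in time to the drug. The operative words are "underlying medical condition, concomitant therapy, or accident and no obvious temporal relationship exists". Possibly related needs some temporal relationship with the cause left ambiguous. Probably related is, on its closing condition, not available when the subject's medical condition can explain the event.

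Section 6.3.6.1 opens with "It is recognized that VOC and pain are frequent and expected events in SCD". It goes on to define new or recurring VOC after discharge as a separate adverse event, graded severe when it needs inpatient treatment. Section 1.2 reports up to 16% of patients readmitted within one week.

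**The concern.** A percentage threshold is there to detect an excess over what the disease produces by itself. Attribution of single cases cannot do that. To a blinded assessor, a readmission caused by the drug and one caused by the disease look alike, and the difference shows only as a rate, chiefly as a difference between arms. Here the rate is computed after the single-case judgment has removed some of the events. Two of the three criteria are, or include, outcomes of the disease, so for those two the filter removes the kind of event that the threshold is meant to count. The infection criterion is less clearly a disease outcome and the argument is weaker there.

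At stake is the only numerical safeguard in the section. If the drug raised early recurrence or mortality, the thresholds could stay uncrossed while the crude rates were well above them.

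**Working it through.** The protocol gives no operating characteristics for the halt criteria, so there is no figure to reproduce.

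**Inputs from the protocol.** 1:1 allocation (section 3); about 76 subjects (8.3.2); DSMB safety reviews at 25 and 50 treated subjects (6.3.6.4); thresholds above 30% and above 5% (6.3.6.4); background readmission up to 16% (1.2).

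**Assumptions, not in the protocol.** The share *q* of events judged possibly or probably related; readmission on active of 32%, 48% or 64% with placebo at 16%; deaths at 10% on active and 1% on placebo.

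**Step 1: events needed.** Above 30% means at least 8 of 25, 16 of 50 or 23 of 76. Above 5% means at least 2 of 25, 3 of 50 or 4 of 76.

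**Step 2: counted rate.** Counted rate = *q* × (active rate + placebo rate)/2. With 48% and 16% the pooled rate is 32%. The counted rate is then 32% at *q* = 100%, 24% at 75%, 16% at 50% and 8% at 25%. At *q* = 50% the threshold, filtered, has the same chance of firing as an unfiltered count of a trial at the 16% background.

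**Step 3: crude rate needed.** For the expected counted rate to reach 30%, the crude rate must be 30%/*q*: 40% at *q* = 75%, 60% at 50% and 100% at 30%. Below *q* = 30% the expected counted rate cannot reach the threshold.

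**Step 4: chance of crossing 30%, exact binomial, both arms pooled.**

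| Active / placebo | q | n = 25 | n = 50 | n = 76 |
|---|---|---|---|---|
| 32% / 16% | 100% | 23% | 12% | 13% |
| 32% / 16% | 50% | 0.7% | 0.02% | <0.01% |
| 48% / 16% | 100% | 57% | 55% | 67% |
| 48% / 16% | 75% | 23% | 12% | 13% |
| 48% / 16% | 50% | 3.6% | 0.4% | 0.1% |
| 48% / 16% | 25% | 0.05% | <0.01% | <0.01% |
| 64% / 16% | 100% | 85% | 90% | 97% |
| 64% / 16% | 50% | 11% | 3% | 2% |

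If the threshold is read on the active arm alone (38 subjects, 48%), the chance is 99% at *q* = 100%, 18% at 50% and 0.1% at 25%.

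**Step 5: deaths.** Pooled rate (10% + 1%)/2 = 5.5%. The chance of exceeding 5% at 50 subjects is 52% at *q* = 100%, 16% at 50% and 3% at 25%.

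**Step 6: false crossings if every event counts.** With 16% in both arms, the chance of exceeding 30% is 3.6% at 25 subjects, 0.4% at 50 and 0.1% at 76. If the percentage were checked after every subject, the chance of crossing at some point up to 76 would be about 49% counting from the first subject and about 6% counting from the 25th.

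**The case against.** **The scale does not send every disease-explained event to unrelated.** That grade also needs the absence of an obvious temporal link, and possibly related is enough for the threshold. This stands. A readmission soon after the last dose can fairly be graded possibly related. The opening is narrower for later events: with the 7.70-hour half-life of Table 4, three days is 72/7.70 = 9.4 half-lives, leaving about 0.15% of drug, and section 1.7.3 reports faster clearance during VOC. An assessor could then find neither limb against an unrelated grade.

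**Section 6.3.6.1 does not tell anyone to call recurrent VOC unrelated.** This also stands. Its remark on frequent and expected events concerns VOC and pain present at baseline, and it treats post-discharge VOC as an adverse event.

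**Other routes do not depend on relatedness.** Readmissions and deaths are serious adverse events, reported whatever their attribution (6.3.6.3). The Medical Monitor reviews all of them continuously and takes concerns to the DSMB, which reviews safety by arm. An investigator may halt a site and the sponsor may halt the study (6.3.6.4). A reader might infer that a drug that worsens the disease could never be detected, or that the scheduled DSMB reviews are the sole safeguard. The protocol does not support either. These routes still do not repair the thresholds: the Medical Monitor is blinded, and the discretionary halts carry no number. After the review at 50, none tied to all-age counts is scheduled for the last 26 of 76 subjects (34%).

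**The assessor is unnamed.** The wording echoes the case grades but could be read as one judgment on the aggregate. On that reading, relatedness would have to be settled before the review meant to examine it.

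**Part of the insensitivity is the 30% level itself.** True: with readmission doubled and every event counted, the chance of crossing at the three sizes is only 12% to 23%. Changing the filter does not alter that.

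**Conclusion.** The point holds in limited form. The relatedness condition in 6.3.6.4 and the grade definitions in 6.3.5.2 fit badly with criteria that name disease outcomes, and the thresholds lose most of their sensitivity if a sizeable share of events is graded unrelated. In the illustration (48% against 16%, 50 subjects) the chance of crossing falls from 55% to 12% when a quarter of events is excluded and to 0.4% when half is.

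The size depends on the share attributed and on the active-arm and death rates, all of them assumed; the 16% background is the protocol's upper figure. If nearly all such events were graded possibly related, little would be lost. It would therefore go too far to say that the thresholds cannot fire at any observed frequency. The direction does not depend on the assumptions: the filter can only lower the count. This is a change the sponsor should make, not a flaw that leaves harm undetectable.

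**What to change.** Reconcile section 6.3.6.4 with section 6.3.5.2 so that the frequency count that calls the DSMB review does not depend on individual blinded attribution. Relatedness would then be judged within that review, where the DSMB may already see unblinded data. State who makes that judgment. The percentages themselves need not change for this purpose.

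The edit is about one clause. The operating cost is some unscheduled reviews and short enrolment pauses, mainly if the percentages are applied at very small numbers: at the 16% background, about half of trials would cross 30% at some point when counting from the first subject, against about 6% when counting from the 25th. The text should therefore also say from what number of subjects the percentages are read.
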